# In the Event of Infusion Prolongation

Any assessments to be performed or samples to be collected (e.g., vital signs, PK) at the end of or following EOI will still be performed or collected beginning at the delayed EOI timepoint. In situations where collection of late day samples, in particular the 4h sample, is logistically difficult due to clinic staff availability, an "end of day" sample may be obtained at the latest practical time on the day of the reaction.

Rechallenge with a shorter duration of infusion (no less than 2 hours) may be attempted at the Investigator's discretion, after a minimum of 2 doses with no evidence of infusion-related toxicity.

All infusion interruptions and subsequent prolongations, including modified infusion times, as well as the toxicity that necessitated them, will be clearly documented on the appropriate page of the patient's eCRF.

## **Modification of Infusion Duration for the Trial**

During Phase 1a, the duration of infusion will be prolonged for all subsequent patients entered to the trial in the following situations:

- In the event of a Grade 2 IRR in ≥ two thirds of the patients entered to a cohort, the duration of infusion for subsequent patients entered to the trial will be extended by 30 minutes (or longer, if indicated).
- In the event of a Grade 3 or greater IRR in any patient within a cohort, the duration of infusion for subsequent patients entered to the trial will be extended by 30 minutes (or longer, if indicated). Such a case will also be considered to have met the protocol criteria for a DLT, thus requiring expansion of the cohort

These same criteria will be applied in the event IRRs occur on the extended infusion schedule. In such a case, the duration of infusion for subsequent patients entered to the trial will be extended by 30 minutes (or longer, if indicated).

## APPENDIX H

## Recommendations for Management of Keratitis and Rash

## **Management of Keratitis**

Any symptoms of keratitis (corneal inflammation/corneal ulceration) should prompt a follow-up ophthalmologic evaluation as soon as possible.

## • Grade 1 Keratitis

Will result in treatment with preservative-free artificial tears, ointments, and/or other therapies as clinically indicated, with a follow-up examination within 2 weeks.

#### • Grade 2 Keratitis

Will be managed as described above, with continuation of study drug dosing at the discretion of the investigator. Persistence of Grade 2 keratitis (> 2 weeks), while on therapy will result in immediate interruption of dosing with study drug. Patients may be retreated at the discretion of the investigator, at a reduced dose, after resolution or amelioration of findings to  $\le$  Grade 1 severity.

#### Grade 3 Keratitis

Will result in immediate interruption of study drug dosing. Patients may be retreated at the discretion of the investigator, at a reduced dose, after resolution or amelioration of findings to  $\leq$  Grade 1 severity.

Patients with persistent  $\geq$  Grade 2 keratitis after  $\frac{7 \text{ days}}{1 \text{ days}}$  of interrupted dosing will be discontinued from further participation in the trial, with scheduled follow-up ophthalmologic assessments at a frequency deemed medically appropriate.

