### 6.7.5 Retreatment Following a Response

Treatment with AVID100 may be restarted in a patient who:

- Previously achieved a documented OR on this study, stopped treatment, and subsequently progresses, or
- Discontinued therapy for a reason other than a DLT or PD, and in whom documented OR or prolonged SD is subsequently noted.

Such action may be taken at the Investigator's discretion, following discussion with the Medical Monitor, provided retreatment criteria are met, no anti-cancer treatment was administered since the last dose of AVID100, and the trial is still open. This option for retreatment does not apply to patients who previously experienced an unacceptable toxicity that required permanent discontinuation of study drug (see **Section 9.1 #1**; Criteria for Treatment Discontinuation).

Retreatment with AVID100 may be initiated at the same dose and infusion duration established for that patient during their previous course of treatment, and on the same schedule, unless dose reduction is necessary.

The same evaluations required during previous treatment will be conducted during subsequent cycles, at the frequencies indicated.

Retreatment cycles of AVID100 may continue to be administered if tolerated and in the absence of further disease progression, at the Investigator's discretion, as long as retreatment criteria continue to be met.

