#### 6.8.3 Definition of DLT

Any of the following toxicities, if judged to be associated with study drug (i.e., possibly related, probably related, or related), will be considered a DLT for the purposes of this trial.

- 1. Evidence of pulmonary fibrosis, any grade (patient must be permanently discontinued)
- 2. Grade 3 non-hematologic toxicity regardless of duration, with the exceptions of:
  - Grade 3 nausea, vomiting, diarrhea, or fatigue lasting  $\leq$  2 days with best supportive care
  - Grade 3 asymptomatic electrolyte abnormalities that are not considered clinically significant by the Investigator and that are controlled with medical therapy
- 3. AST and/or ALT elevation  $> 3 \times \text{ULN}$  (or  $> 3 \times \text{baseline}$  if elevated at study entry as allowed by study eligibility criteria; see **Section 4.3.1** #7), with total bilirubin  $> 2 \times \text{ULN}$  without initial findings of cholestasis (i.e., no elevation in serum alkaline phosphatase [ALP]), that cannot be explained by other factors
- 4. Any Grade 4 non-hematologic toxicity with the exception of:
  - Grade 4 asymptomatic electrolyte abnormalities lasting < 7 days that are not considered clinically significant by the Investigator and that are controlled with medical therapy
- 5. Neutropenia that is:
  - ≥ Grade 3 and associated with fever (ANC < 1000 per mm³; temperature > 38.3°C [101°F] or a sustained temperature of ≥ 38 °C [100.4°F] for > 1 hour ) (i.e., febrile neutropenia)
  - Grade 4 and sustained (ANC < 500 per mm^3, duration > 5 days)
- 6. Thrombocytopenia that is:
  - Grade 3 with clinically significant hemorrhage or requirement for transfusion

- Grade 4 (platelets < 25,000 per mm^3)
- 7. Inability to complete Cycle 1 at the assigned dose (i.e., receipt of < 1 full planned dose of study drug plus 3 weeks of follow-up due to  $\geq$  Grade 3 toxicity)
- 8. Treatment delays > 2 weeks from the scheduled "next dose" due to ≥ Grade 3 toxicity Other toxicities may be considered a DLT as determined by the Investigator in conjunction with the Medical Monitor.

The above criteria will be used to make individual patient determinations regarding dose reductions, interruptions, or discontinuation throughout the course of the trial, but *only those DLTs occurring during Cycle 1* will be used to make decisions regarding cohort dose escalation and tolerability.

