## 7.3.1 Ophthalmology Examination

(To include slit lamp evaluation, tests to evaluate corneal integrity and visual acuity assessment)

- Screening
- End of Cycle 2\*,\*\*
- EOT\*\*
- As clinically indicated

\*When evaluating QTc, baseline should be considered the ECG immediate preceding the start of study drug infusion on the day of assessment.

\*\*In the event of significant electrolyte abnormalities, the evaluation frequency should be increased to include additional evaluations between the scheduled assessments, as clinically indicated

\*End of Cycle assessments may be conducted at any time during the week prior to Day 1 of the next cycle.

\*\*May be combined if patient discontinues treatment at End of Cycle 2

Note: See Appendix H (Recommendations for Management of Keratitis and Rash) for dose modification instructions for keratitis (corneal inflammation/ulceration)

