#### 8.1. Determination of DLT versus Non-DLT

When an AE occurs, the Investigator will also determine whether the protocol definition of a DLT is met (Section 6.8.3). If so, the patient will be either discontinued from treatment or may continue treatment if there is evidence of an OR, SD, or other clinical benefit, but must do so at a reduced dose of study drug, and ONLY following discussion with the Sponsor's Medical Monitor(s). Patients may not be retreated following the occurrence of a DLT until retreatment criteria have been met (Section 6.7.1).

Alternatively, the Investigator may determine that the toxicity does not meet the protocol definition for DLT, but nevertheless warrants dose modification, because it is:

- Not controlled by optimal supportive care, or
- Not tolerated due to symptomatology or interference with normal daily activities

For toxicity that does not meet the protocol definition of DLT, the Investigator may, as described below, elect to prolong the infusion duration (for IRRs), reduce the dose of study drug, and/or temporarily delay dosing with study drug in order to allow for amelioration of the toxicity.

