### 9.1. Criteria for Treatment Discontinuation

Patients will be discontinued from further treatment with study drug in the event of any of the following:

- 1. Patient must be permanently discontinued in the event of any major, potentially irreversible organ system DLT, including:
  - Pulmonary toxicity defined as:
    - o Evidence of pulmonary fibrosis, any grade
    - o Reduction of forced vital capacity (FVC) or DLco  $\geq$  Grade 3
  - Neurotoxicity defined as peripheral neuropathy ≥ Grade 3
  - Any ocular toxicity  $\geq$  Grade 3
  - Nephrotoxicity defined as:
    - Acute kidney disease  $\geq$  Grade 3 (i.e., creatinine  $> 3 \times$  baseline or > 4.0 mg/dL)
    - o Chronic kidney disease ≥ Grade 3 (i.e., estimated glomerular filtration rate [eGFR] or creatinine clearance [CrCl] 29-15 mL/min/1.73 m²)
    - o Proteinuria  $\geq$  Grade 3 (i.e.,  $\geq$  3.5 g/24 hours)
  - Hepatotoxicity suggestive of drug-induced liver injury, as characterized by the following 3 criteria:
    - AST and/or ALT elevation  $> 3 \times ULN$  (or  $> 3 \times$  baseline if elevated at study entry as allowed by study eligibility criteria; see **Section 4.3.1** #7)
    - Total bilirubin  $> 2 \times ULN$  without initial findings of cholestasis (i.e., no elevation in serum ALP)
    - No explanation for the above findings, such as: viral hepatitis A, B, or C; preexisting or acute liver disease; or another drug capable of causing the observed injury

Adapted from: Hy's Law. Drug-induced liver injury: premarketing clinical evaluation. Guidance for Industry. U.S. Department of HHS, FDA, CDER, CBER, 2009.

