# **FORBIUS**

2. Any other DLT (see **Section 6.8.3**; Definition of DLT) considered by the Investigator to require treatment discontinuation.

Note: Patients experiencing a DLT not listed in #1 above may continue at a reduced dose if there is evidence of an OR, SD, or other clinical benefit, provided protocol stipulated retreatment criteria delineated in **Section 6.7.1** (Retreatment Guidelines) have been met, and ONLY following discussion with the Sponsor's Medical Monitor(s)).

3. Another AE not meeting the criteria for a DLT, yet considered by the Investigator to require treatment discontinuation.

Note: AEs resulting in a patient's permanent discontinuation from study treatment, regardless of seriousness or relationship to study drug, MUST be reported promptly to the Sponsor (or designee).

- 4. Documented progressive disease at any time during the study
- 5. Treatment failure not meeting the criteria for progressive disease, but considered by the Investigator to require treatment discontinuation.
- 6. Requirement for a significant surgical procedure

Note: Patients requiring a minor surgical procedure (e.g., port placement, skin abscess drainage) may continue at the Investigator's discretion following discussion with the Sponsor's Medical Monitor(s). A brief interruption in therapy may be considered.

- 7. An intercurrent illness which, in the opinion of the Investigator, would prevent completion of study-related evaluations
- 8. Significant deviation from the protocol or eligibility criteria. Such patients will be considered protocol violations and will be discontinued from treatment
- 9. Pregnancy
- 10. Noncompliance with study or follow-up procedures
- 11. Patient withdrawal of consent and election to discontinue treatment with study drug. (Patients may leave the study at any time for any reason if they wish to do so, without any consequence.)
- 12. Termination of the study by the Sponsor
- 13. Any other reason which, in the opinion of the Investigator, would justify treatment discontinuation. In such a case, the Investigator's reason for treatment discontinuation must be recorded on the appropriate page of the eCRF.

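### Appendix H lets a patient resume at a reduced dose after drug-related Grade 3 keratitis, an event for which Section 9.1 #1 requires permanent discontinuation

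*Combined protocol and SAP*

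**What the plan says.** Appendix H, under Grade 3 Keratitis, calls for immediate interruption "of study drug dosing. Patients may be retreated at the discretion of the investigator, at a reduced dose, after resolution" or improvement to Grade 1 or less. A second paragraph takes the patient off the trial if keratitis of Grade 2 or above persists after 7 days of interrupted dosing. Neither paragraph mentions relationship to study drug or Section 9.1. Section 7.3.1 points the site to this appendix "for dose modification instructions for keratitis (corneal inflammation/ulceration".

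Section 9.1 #1 opens: "Patient must be permanently discontinued in the event of any major, potentially irreversible organ system DLT, including". Its list contains "Any ocular toxicity" of Grade 3 or above. The note to 9.1 #2 says "Patients experiencing a DLT not listed in #1 above may continue at a reduced dose", subject to further conditions. Section 3.3 (Study Assessments) names ocular toxicity among the exceptions to reduced-dose continuation and says such patients must stop permanently.

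The synopsis version of the discontinuation criteria lists pulmonary, neurological, renal and hepatic toxicity but has no ocular item.

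**The concern.** An investigator who sees a drug-related Grade 3 corneal event finds two instructions. One says the patient must not receive study drug again. The other lets the investigator restart at a lower dose once the eye has recovered. Section 7.3.1, the section governing eye examinations, leads to the second.

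At stake is re-exposure of a patient whom the sponsor has elsewhere said must stop, and different handling of the same event at different sites. Corneal toxicity is an anticipated risk: Section 2.3.1.3 names keratitis as a toxicity of the anti-EGFR antibodies, the GLP monkey studies found corneal epithelial changes, and a history of corneal disorders is an exclusion criterion.

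**Working it through.** No arithmetic decides this point; it is a comparison of texts.

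**Step 1. Is drug-related Grade 3 keratitis a DLT?** Section 6.8.3 applies to toxicities judged possibly related, probably related or related to study drug. Item 2 covers Grade 3 "non-hematologic toxicity regardless of duration, with the exceptions of" short-lived nausea, vomiting, diarrhea or fatigue, and asymptomatic electrolyte abnormalities. Keratitis is non-hematologic and in neither exception. It is a DLT.

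**Step 2. Is that DLT on the permanent-discontinuation list?** Yes. The ocular item in 9.1 #1 covers every ocular toxicity of Grade 3 or above and makes no allowance for events that later resolve.

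**Step 3. Is another route to a reduced dose open?** Section 8.1 states the general rule that a patient with a DLT "may continue treatment if there is evidence of an OR, SD, or other clinical benefit, but must do so at a reduced dose", after discussion with the Medical Monitor. The note to 9.1 #2 confines that route to DLTs not listed in #1, and Section 3.3 removes ocular toxicity by name. The route is closed.

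**Step 4. What does Appendix H allow for the same event?**

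| Grade 3 keratitis | Sections 9.1 and 3.3 | Appendix H |
|---|---|---|
| Drug-associated | Permanent discontinuation | Interrupt; reduced-dose retreatment at the investigator's discretion after recovery to Grade 1 or less |
| Not drug-associated | Not a DLT, so 9.1 #1 does not apply | Same as above |

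The first row is a contradiction. The second is not.

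**Step 5. How often might it arise?** Table 1 lists treatment-related events in 24 Phase 1a patients. Read as well as its broken layout allows, it shows one keratitis, at Grade 2, and no ocular event at Grade 3. Section 2.6 describes only 6 patients evaluated at 220 mg/m². In the visible part of Table 2 (Phase 2a, 13 patients as of 15 April 2020), the eye events (uveitis, eye pain/irritation, conjunctival injection) stand in the Grade 2 row; rows for higher grades are not in the available text.

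**The case against.** The strongest reply is that the protocol already tells the site which text governs. The opening of Section 8 says that events requiring discontinuation are set out in Section 9.1. Sections 9.1 and 3.3 are mandatory; Appendix H is titled as recommendations and its retreatment sentence is permissive. The sponsor should also hear of each step: Section 6.10 requires prompt reporting of DLTs, Section 8.3.2 of every interruption and Section 8.3.3 of every dose reduction.

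Most of this stands. A reader might infer that nothing in the protocol indicates which text prevails; the Section 8 sentence does not support that. It is a pointer, though, not a precedence rule, and Section 7.3.1 describes Appendix H as giving dose modification instructions. Reporting makes an error more likely to be caught but does not reconcile the texts.

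Three other stronger readings also fail:

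- *All Grade 3 keratitis is mishandled.* Section 9.1 #1 covers DLTs, and a DLT must be drug-associated. For unrelated keratitis, Appendix H conflicts with nothing in 9.1 #1.
- *Section 6.7.5 separately bars this retreatment.* Its bar attaches to the restart option in that section (progression after an earlier response, or response or prolonged stable disease noted after stopping for reasons other than a DLT or progression). It does not govern resumption after an adverse-event interruption.
- *The Grade 3 text in Appendix H should be deleted.* That would strip unrelated Grade 3 keratitis of its interruption and recovery conditions. Removing the 7-day sentence, worded for Grade 2 or above, could also loosen the handling of Grade 2 keratitis.

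**Conclusion.** The conflict is real and limited to study drug-associated Grade 3 keratitis. For that event, Appendix H permits what Section 9.1 #1, the 9.1 #2 note and Section 3.3 prohibit. It merits correction because the change is small and the consequence is a patient-safety one.

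The number affected is likely to be small: the event must be Grade 3 keratitis, be judged drug-associated, recover to Grade 1 or less, and then be retreated under Appendix H. That judgment rests on Table 1 as legible and on a Phase 2a table only partly available. A reader might want to project an event count for the remaining Phase 2a patients. No Grade 3 ocular events in 24 patients pooled over all doses, with 6 described at the Phase 2a dose, do not support a useful projection for keratitis.

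No sample size, power or error rate changes. The different wording on major surgery in Section 6.12 and Section 9.1 #6 is a separate matter, and this point does not depend on it.

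**What to change.** (a) At the start of the Grade 3 keratitis text in Appendix H, insert: *Study drug-associated Grade 3 or higher keratitis: permanently discontinue study drug per Section 9.1 #1, with follow-up ophthalmologic assessments as medically appropriate.* Limit the existing interruption and reduced-dose retreatment text to Grade 3 keratitis judged not associated with study drug. Keep the 7-day discontinuation sentence for keratitis of Grade 2 or above, and leave the Grade 2 paragraph as it is. The words 'or higher' also cover Grade 4, for which Appendix H has no entry.

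(b) Add *Any ocular toxicity ≥ Grade 3* to the synopsis discontinuation list so that it matches 9.1 #1.

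The cost is amendment wording, with no added procedures or patients. The downside is that a patient whose drug-related Grade 3 keratitis resolves cannot resume study drug, which Section 9.1 already requires.

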## **Management of Rash**

Several different treatment options have been utilized in order to relieve symptoms and improve the rash associated with study drug therapy. **When possible, topical therapy is preferred.** Although no single approach has emerged as superior, recommendations for management are as follows:

## Grade 1Rash

Mild, grade 1 rash has been observed to resolve without intervention.

#### Grade 2 Rash

May be treated according to current standard of care

• Grade 3 (or greater) Rash (or intolerable Grade 2 Rash)

Will result in dose reduction of study drug and treatment.

## **APPENDIX I**

## Sample Size Considerations

The sample size considerations are presented for estimation and testing with respect to the response rate for efficacy, i.e., inference regarding the true probability of response. The normal approximation to the binomial distribution is used, unless otherwise specified.

Let  $\pi$  denote the true unknown probability of interest. The goal is to conclude that this probability exceeds a specified value ( $\pi$ 0).

Testing the null hypothesis H0:  $\pi = \pi 0$  against the one-sided alternative hypothesis H1:  $\pi > \pi 0$  can be used to achieve this goal. This test is performed at the 2.5% level, which is equivalent to testing the two-sided alternative at the 5% level.

The test procedure is to conclude that the observed result is statistically significant if:

$$n1/2 (p-\pi 0)/(p(1-p))1/2 > 1.96$$
,

where p is the observed proportion of responses from n subjects.

The smallest value of p required to have statistical significance for specified values of  $\pi 0$  and n is the solution to this inequality, but a "closed expression" is not possible. This value of p is determined by evaluating n1/2 (p- $\pi 0$ )/(p(1-p))1/2 and then comparing this value to 1.96, and is given in the following table.

SMALLEST VALUE OF P (%) FOR STATISTICAL SIGNIFICANCE (Level 0.05, 2-Sided)									
πο	π 0 N=15 N=20 N=34 N=40								
0.20	45.2	41.7	36.2	35.0					
0.25	50.4	46.9	41.6	40.2					
0.30	55.2	51.9	46.8	45.5					
0.35	59.9	56.8	51.8	50.5					
0.40	64.3	61.4	56.7	55.5					
0.45	68.6	65.8	61.4	60.2					
0.50	72.6	70.1	66.0	64.9					

Other alternatives for this examination are power considerations: (1) determination of power for specified n and assumed true value of  $\pi$ , (2) determination of n required to have power 80% or 90% for assumed true value of  $\pi$ , and (3) determination of  $\pi$  for specified n and power. The latter is related to a confidence interval (CI) because it is estimation of  $\pi$ , so the 95% CI is presented for specified values of the observed proportion of responses from n subjects (p); this is also related to the values given in the first Table. In addition to the 95% CI using the normal approximation, the 95% CI using the exact binomial method is also presented as these are presented in the protocol for p=15% and 25%.

Power (%) for specified n and sample size (n) required for power 80% or 90% for assumed true value of the true probability of response ( $\pi$ ) are given in the following table.

POWER (%) FOR SPECIFIED N					SAMPLE SIZE FOR SPECIF	_	
Null (π 0 )	True (π)	N=15	N=20	N= 34	N=40	Power=80%	Power=90%
0.20	0.30	13.2	16.3	24.6	28.1	165	221
	0.35	22.9	29.0	45.0	51.2	80	107
	0.40	35.2	44.7	66.3	73.3	48	64
	0.45	49.5	61.3	83.4	88.8	32	42
	0.50	64.2	76.5	93.8	96.7	22	30
	0.55	77.8	88.2	98.4	99.4	16	22
	0.60	88.5	95.5	99.7	99.9	12	16
0.25	0.45	34.3	43.6	65.0	72.0	49	66
	0.50	0.491	60.9	83.0	88.5	32	43
	0.55	0.646	76.9	94.0	96.8	22	29
	0.60	0.790	89.2	98.6	99.5	16	21
0.30	0.50	0.341	43.2	64.5	71.6	50	66
	0.55	0.495	61.3	83.4	88.8	32	42
	0.60	0.660	78.2	94.6	97.2	21	29
	0.65	0.811	90.7	99.0	99.6	15	20
0.35	0.55	0.343	43.6	65.0	72.0	49	66
	0.60	0.507	62.6	84.5	89.8	31	41
	0.65	0.683	80.3	95.6	97.8	20	27
0.40	0.60	0.352	44.7	66.3	73.3	48	64
	0.65	0.528	65.0	86.4	91.2	29	39

\* Computed using EAST 6.4

	95% CI FOR PROBABILITY OF RESPONSE (Π;% )							
	N	ormal Approxin	nation to Binomi	al	Exact Binomial			
р	N=15**	N=20	N=34**	N=40	N=15	N=20	N=40	
10%	(0, 25.2)*	(0, 23.1)*	(0, 20.1)*	(0.7, 19.3)		(1.2, 31.7)	(2.8, 23.7)	
15%	(0, 33.1)*	(0, 30.6)*	(3.0, 27.0)	(3.9, 26.1)		(3.2, 37.9)	(5.7, 29.8)	
20%	(0, 40.2)*	(2.5, 37.5)	(6.6, 33.4)	(7.6, 32.4)	(4.3, 48.1)	(5.7, 43.7)	(9.1, 35.6)	
25%	(3.1, 46.9)	(6.0, 44.0)	(10.4, 39.6)	(11.6, 38.4)		(8.7, 49.1)	(12.7, 41.2)	
30%	(6.8, 53.2)	(9.9, 50.1)	(14.6, 45.4)	(15.8, 44.2)		(11.9, 54.3)	(16.6, 46.5)	
35%	(10.9, 59.1)	(14.1, 55.9)	(19.0, 51.0)	(20.2, 49.8)		(15.4, 59.2)	(20.6, 51.7)	
40%	(15.2, 64.8)	(18.5, 61.5)	(23.5, 56.5)	(24.8, 55.2)	(16.3, 67.7)	(19.1, 63.9)	(24.9, 56.7)	

p= Observed Proportion

From epitools.ausvet.com.au

The overall sample size for the Phase 2a Expansion Cohorts will be approximately 60 patients treated at the RP2D, with accrual to be divided among up to 3 cohorts (tumor types mTNBC, SCCHN, and Sq-NSCLC); additional patients may be entered to the Phase 2a Expansion Cohorts if fewer than 30 patients are required to establish the RP2D in Phase 1a.

The current planned initial enrollment of 15 patients per cohort (or in each subcohort in the case of TNBC) may be expanded based on initial observation of > 2 objective responses (13% ORR) in any of the three indications (two separate cohorts in TNBC) to be studied. This sample size has a 35.2% power to detect a 40% ORR compared to a potential control response of 20% at a two-sided 0.05 level of significance. In addition, the power is between 45-54% to detect objective response rates between 20 to 40% in a 15 patient cohort at a two-sided 0.05 level of significance. After evaluation of the initial ORR in each cohort a decision will be made to either continue to include patients with treatment-refractory advanced/metastatic malignancies without other therapeutic options on an open-label trial (e.g., if the objective response rate  $\geq$  20% and responses are durable), consider alternative trial designs for further exploration of efficacy in any of the indications, or discontinue development if fewer than two (0 or 1) responses are observed in any of the three initial fifteen patient cohorts. The durability of objective responses

\* Computed lower limit is negative.

\*\* Not all observed proportions given above are possible for n=15 and n=34

and disease stabilization > 8 weeks will also be considered in the decision to expand cohorts or pursue other options for further development in any of the three indications.

TEST OF NULL AT 0.05 LEVEL (TWO SIDED) USING NORMAL APPROXIMATION								
	Power (%	) for specified N (	Computed using E	AST 6.4)				
Null (π 0 )	Null $(\pi_0)$ True $(\pi)$ N=15 N=20 N=34 N=40							
0.20	0.30	13.2	16.3	24.6	28.1			
	0.40	35.2	44.7	66.3	73.3			
	0.50	64.2	76.5	93.8	96.7			
	0.60	88.5	95.5	99.7	99.9			

